### 1 INTRODUCTION

Unless noted otherwise, the information provided in Section 1 was excerpted from the Investigational Brochure for PK10571.

#### 1.1 Background

Gossamer Bio, Inc. plans to develop PK10571 for the treatment of pulmonary arterial hypertension (PAH), an orphan disease associated with high morbidity and mortality. Despite recent advances in vasodilator therapy for PAH, more effective treatments are needed.

PK10571 has not been previously studied in humans.

#### 1.1.1 Pharmacology

PK10571 is a potent and selective tyrosine kinase inhibitor which has shown efficacy in animal models of PAH.

The following studies of PK10571 have been performed:

- In vitro kinase assays
- In-cell Westerns to measure inhibition of platelet-derived growth factor BB (PDGFBB) stimulated AKT (also known as protein kinase B) phosphorylation
- Enzyme-linked immunosorbent assays (ELISA) to estimate IC50 for inhibition of phosphorylation of PDGF receptors in human lung fibroblasts
- Endothelial cell permeability assays
- Human ether-à-go-go-related gene (hERG) channel activity assay
- Metabolism study in human hepatocytes
- Biliary excretion study
- Metabolism in lung microsomes
- Preclinical efficacy study in the rat monocrotaline plus pneumonectomy model
- Preclinical efficacy study in the rat Sugen 5416 (SU5416) hypoxia model
- Platelet aggregation studies

PK10571is well absorbed from the lung

in both rats and dogs and accumulation did not

appear to be an issue in either species.

Gossamer Bio, Inc.

Gossamer Bio, Inc.

CONFIDENTIAL

31 Jul 2018

Page 6

[figure not shown]

Gossamer Bio, Inc.

CONFIDENTIAL

31 Jul 2018

Page 7

### **1.2 Dose Selection Rationale**

The first in human exposure of PK10571 will be a single dose ranging study followed by multiple dose (7 day) administration in healthy volunteers. The results from the preclinical program were used to select the starting dose for this phase IA clinical trial.

The starting dose is based on the Food and Drug Administration (FDA) Guidance for Industry "Estimating the Maximum Safe Starting Dose in Initial Clinical Trials for Therapeutics in Adult Healthy Volunteers" dated July 2005.

Gossamer Bio, Inc.

[figure not shown]

Gossamer Bio, Inc.

CONFIDENTIAL

31 Jul 2018

Page 9

Gossamer Bio, Inc.

CONFIDENTIAL

Page 10

Escalation will be carried out with careful clinical monitoring and in accordance with dose escalation and halting rules described in the protocol. It should be noted that if a higher maximum dose of is warranted in the clinical trial, the nonclinical data would also support this dose with an animal:human dose multiple of 15.

### **1.3** Study Rationale

Because PAH represents a serious orphan medical condition with a critical need for better therapies, Gossamer Bio, Inc. plans to work closely with the Food and Drug Administration (FDA) in order to ensure an efficient development program.

Gossamer Bio, Inc. will evaluate PK10571 in an initial Phase 1A single-dose/multipledose study in normal, healthy volunteers,

Part A of the phase 1A study is a single ascending dose (SAD) double-blind, placebocontrolled randomized trial of inhaled dry powder PK10571 in healthy human volunteers for determination of safety. Part A will consist of at least 4 cohorts and up to 5 cohorts. Within each cohort, subjects will be randomly assigned to receive either active drug or placebo. The initial dose will be determined based on the results of animal toxicology studies.

After completion and review of the SAD trial (Part A), the multiple ascending dose (MAD) clinical trial (Part B) will be performed. The MAD clinical trial is a doubleblind, placebo-controlled randomized repeat dose trial of inhaled dry powder PK10571 in healthy human volunteers. There will be up to 3 dose cohorts, and within each cohort subjects will be randomly assigned to receive either active drug or placebo. Study subjects will be administered active drug or placebo once daily for 7 days.

Gossamer Bio, Inc.

### **2 OBJECTIVES**

The objectives of this study are:

- To determine the safety and tolerability of single ascending inhalation doses of PK10571 formulated as a dry powder with excipient L-leucine in healthy adult subjects (Part A)
- To determine the safety and tolerability of multiple ascending inhalation doses of PK10571 formulated as a dry powder with excipient L-leucine in healthy adult subjects (Part B)
- To evaluate the bioavailability of PK10571 following single- and multiple-dose regimens
- •

### **3 STUDY DESIGN SUMMARY**

This is a first-in-human, single-center, randomized, double-blind, placebo-controlled, two-part study in healthy adult males and females of non-childbearing potential. Because the safety profile of PK10571 in humans is unknown and this is the first clinical study to assess PK10571 in humans, a single-ascending dose escalation design will be used in Part A of the study. Part B will be a multiple-ascending dose escalation design, to be run only after review of safety and pharmacokinetic data from Part A.

In the single ascending dose study (Part A) at least 4 dose levels of PK10571 will be tested:

An optional fifth dose level of up to may be added, based on safety and pharmacokinetic data from the first 4 cohorts. Subjects will be randomized into one dose cohort and receive either PK10571 or placebo. Within each cohort, 6 subjects will receive active drug and 2 subjects will receive placebo.

In the multiple ascending dose study (Part B), up to three dose levels of PK10571 will be tested. The daily dose will be administered daily for 7 days with close clinical monitoring. The dose for the first cohort of Part B will be determined by review of the safety and pharmacokinetic data from Part A by the Safety Review Committee. The dose interval for the first cohort of Part B (i.e., once daily, twice daily, or up to three times daily) will be determined by review of the safety and pharmacokinetic data from Part A by the Safety Review committee. Subsequent doses and dosing intervals will be determined by review of the safety and pharmacokinetic data from the prior cohort.

For both Part A and Part B, for each cohort, randomization will occur in 2 blocks as follows: In the first block, 2 subjects (sentinel subjects) will be randomized 1:1 to receive PK10571 or placebo; in the second block, 6 subjects will be randomized 5 PK10571: 1 placebo. If PK10571 is well-tolerated in the sentinel subjects, the remainder of the cohort (n = 6) will be randomized. There will be a minimum of 48 hours between dosing of the 2 sentinel subjects and the remainder of the cohort.

The safety, tolerability, and pharmacokinetics of PK10571 will be evaluated in each sequential cohort prior to each dose cohort escalation, assessing the totality of all the safety data prior to initiating the next cohort.

Gender distribution will be based on sequential screening of volunteers who meet entry criteria, with a minimum of 4 females per cohort, in order to ensure 2 females per active dose group. Subjects will be assigned numbers in an ascending order, based on successful completion of the screening process. Each subject will participate in only one cohort.

Subjects who withdraw from the study may be replaced at the discretion of the Principal Investigator and Sponsor. Replacement subjects will be given a new randomization number in the 9000 series and assigned to the same treatment as the subject they replace.

Safety assessments will include adverse events; vital signs; oxygen saturation; physical examination; 12-lead electrocardiogram (ECG); clinical laboratory examinations; and pulmonary function tests (spirometry).

Blood and urine will be collected for pharmacokinetic analysis.

Blood will be collected for buffy coat analysis.

### 3.1 Part A

Part A of the study is a single ascending dose study design. Up to 5 dose levels will be studied. Subjects will receive either PK10571

placebo. Part A will enroll up to 40 subjects; 8 subjects per cohort. The data from each cohort will be analyzed before deciding whether to proceed with the next cohort.

Each cohort will include a sentinel group of 2 subjects (1 active and 1 placebo) who will be dosed at least 48 hours before the remaining subjects (5 active and 1 placebo). Dosing of the remaining subjects will occur following a safety evaluation of the sentinel group.

Gossamer Bio, Inc.

CONFIDENTIAL

or

Subjects will receive one of the treatments listed in Table 1. Within each cohort, subjects will be assigned to either active treatment or placebo in randomized fashion.

| Tuble 2 Tute A. Thunked Doses for Conditis 1, 2, and 5  |   |        |               |  |
|---|---|--------|---------------|--|
| Cohort  | Test Formulation Dose   |        | Placebo       |  |
| 1 - starting dose   | PK10571   | (n=6)* | Placebo (n=2) |  |
| 2 - second dose   | PK10571   | (n=6)* | Placebo (n=2) |  |
| 3 - third dose  | PK10571   | (n=6)* | Placebo (n=2) |  |
| 4 – fourth dose   | PK10571 up to   | (n=6)¶ | Placebo (n=2) |  |
| 5 – fifth dose  | PK10571 up to   | (n=6)p | Placebo (n=2) |  |
| FPD = fine particle do  | se; $n =$ number of subjects  |        |               |  |
| * Capsules with a nominal fill weight of the will be administered sequentially to achieve the target FPD for Doses 1-3. |   |        |               |  |
| " I  | Capsules with a nominal fill weight of weight will be administered to achieve the dose for cohort 4 (nominal 18 mg FPD (5 capsules) |        |               |  |
| P The capsule fill weight, FPD, and number of capsules to be administered will be determined to achieve the             |   |        |               |  |

Table 2Part A: Planned Doses for Cohorts 1, 2, and 3

P The capsule fill weight, FPD, and number of capsules to be administered will be determined to achieve the target dose for cohort 5, if the Safety Review Committee decides to proceed with this dose.

Each dose will be administered using an oral inhalation device following a 10-hour overnight fast. After dosing, no food will be allowed until 4 hours postdose. Meals will be standard and scheduled at approximately the same times relative to dose for each cohort.

No water may be consumed for 1 hour prior through 1 hour after dose, except for 60 mL of room temperature water which will be given to subjects to rinse their mouths after dosing. Subjects will swish the 60 mL of water in their mouths then spit it out.

Blood samples for pharmacokinetic evaluation will be obtained prior to dose administration and following dose administration at selected times through 48 hours postdose. A total of 14 pharmacokinetic blood samples will be collected from each subject. Plasma pharmacokinetic samples will be analyzed for PK10571 using a validated analytical method. Appropriate pharmacokinetic parameters will be calculated for each formulation using non-compartmental methods.

Subjects will be housed at the clinical research site for observation for 3 days and then followed up by phone daily for the next 7 days. Subjects will return to the clinical research site for a safety evaluation on Day 11.

### 3.2 Part B

Part B is a multiple ascending dose study design. Subjects will receive either PK10571 or placebo. Approximately 24 subjects will be enrolled in Part B. Subjects will be enrolled in 3 cohorts of 8 subjects each.

Gossamer Bio, Inc.

The initial dose for Part B will be determined after review of the safety and pharmacokinetic data from Part A by the Safety Review Committee.

Data from the lower dose cohort will be analyzed before deciding whether to proceed with the higher dose cohort. Alternatively, a lower dose may be administered, depending upon review of previous cohort's safety and pharmacokinetic data.

Subjects will receive one of the treatments listed in Table 3. The assigned treatment will be given either as a single daily dose (QD), or divided into two daily doses (BID), or divided into three daily doses (TID; each dose to be separated by 6 hours on a given day).

Subjects will be assigned to either active treatment or placebo in randomized fashion.

Table 3Part B: Planned Doses for Cohorts 1–3

| Cohort                 | Test Formulation (n = 6) | Placebo (n = 2) |
|------------------------|--------------------------|-----------------|
| 1                      | PK10571 initial dose     | Placebo         |
| 2                      | PK10571 mid dose*        | Placebo         |
| 3                      | PK10571 high dose*       | Placebo         |
| n = number of subjects |                          |                 |

n = number of subjects

Note: The dosing regimen will be either once daily (QD), twice daily (BID), or three times daily (TID) for 7 consecutive days. For TID dosing, each daily administration will be separated by 6 hours.

\* Alternately, Cohort 2 or 3 will receive a lower dose, depending upon safety and pharmacokinetic data from Cohort 1 or 2, respectively.

Each dose will be administered using an oral inhalation device. Meals will be the same and scheduled at approximately the same times relative to dose for each cohort, if possible. Refer to Section 5.5.1 for details regarding timing of meals for each proposed dosing regimen (QD, BID, and TID).

No water may be consumed for 1 hour prior through 1 hour after each dose, except for 60 mL of room temperature water which will be given to subjects to rinse their mouths after dosing. Subjects will swish the 60 mL of water in their mouths then spit it out.

Blood samples for pharmacokinetic evaluation will be obtained before the first dose of the day on Day 1 and Day 7 and at selected times through 36 hours after the first dose on Day 1, before the first dose on Days 3-6, through 36 hours after the first dose on Day 7, and on Day 9, Day 10, Day 14, and Day 35.

For QD dosing, a total of 34 pharmacokinetic blood samples will be collected from each subject in Part B.

For BID dosing, a total of 30 pharmacokinetic blood samples will be collected from each subject in Part B.

Gossamer Bio, Inc.

For TID dosing, a total of 30 pharmacokinetic blood samples will be collected from each subject in Part B. Plasma pharmacokinetic samples will be analyzed for PK10571 using a validated analytical method. Appropriate pharmacokinetic parameters will be calculated for each formulation using non-compartmental methods.

Subjects will be housed at the clinical research site for observation until Day 9 (48 hours after the last dose) and return to the clinical research site for safety evaluation and pharmacokinetic blood collection on Days 10, 14, and 35.

### 3.3 Safety Review Team

A Safety Review Committee consisting of the Principal Investigator or designee (e.g., a medically qualified sub-investigator) and Sponsor representatives with appropriate expertise will meet and review, at minimum, the 24-hour safety data for the sentinel group of each cohort in Part A prior to dosing the remainder of the cohort.

The Safety Review Committee will review the safety and pharmacokinetic data from each cohort in Part A. Dose escalation to the next level will occur only after review of the 24-hour pharmacokinetic data, and safety data up to and including Day 11 from the preceding cohort(s). The factors to be used in determining the next incremental dose are described in Section 3.4. There will be at least 2 weeks between dosing of each cohort.

The Safety Review Committee will review the safety and pharmacokinetic data of Part A before starting Part B. The pharmacokinetic data from the first 24 hours of Part B, Cohort 1 up to and including Day 7, and the safety data up to and including Day 14 will be reviewed prior to dosing of Part B, Cohort 2.

All available safety data will be assessed prior to each dose escalation, including but not limited to the following:

- All adverse events (AEs)
- Safety laboratory tests (i.e., hematology, chemistry and urinalysis)
- Coagulation tests
- Vital signs
- Physical examinations
- ECGs (12-lead)
- Pulmonary function tests (spirometry)

If the initial dose administered to Cohort 1 is not tolerated, a lower dose cohort may be allowed.

In subsequent cohorts, the dose may be decreased from the planned dose depending on results of safety and pharmacokinetic data.

Gossamer Bio, Inc.

#### CONFIDENTIAL

31 Jul 2018

#### **3.4 Dose Escalation**

Dose escalation will proceed after the review of all available safety data from subjects in the preceding cohort(s) is completed, the assessment has determined that the prior dose(s) is/are safe, and escalation to the next dose level is recommended.

The following factors will be considered for determining the next incremental dose:

- 1. Observation of clinical adverse effects based on symptoms and signs;
- 2. Observed abnormalities in clinical chemistries, complete blood count (CBC), liver function tests, or coagulation tests;
- 3. Pharmacokinetic parameters: maximum concentration  $(C_{max})$  and area under the plasma versus concentration curve (AUC).
- 4. For Part A, if no adverse effects are observed at the starting dose the third dose will be the next dose will be (2 times the second dose), the fourth dose will be up to (up to two times the third dose), and the fifth dose will be up to (one and a half times the fourth dose).
- 5. For Part B, if no adverse effects are observed at the starting dose regimen (whether QD, BID, or TID), then the next dose will be a mid-dose to be determined by the Safety Review Committee, and if no adverse effects are seen at the mid-dose, then the next dose will be higher dose to be determined by the Safety Review Committee. In the event of adverse effects at a given dose the Safety Review Committee may recommend a decrease in dose for the next dosing cohort.

### **3.5 Stopping Rules for Dose Escalation**

The following will result in a decision not to continue dose escalation if judged by the Safety Review Committee to be related to study drug:

- 1. Onset of respiratory symptoms postdose suspected to be related to study medication including but not limited to bronchospasm (wheezing), stridor, clinically significant moderate dyspnea, oxygen desaturation with dyspnea, evidence of significant airflow obstruction on spirometry in at least 2 subjects.
- 2. Three-fold increase in aspartate transaminase (AST) or alanine transaminase (ALT) above the upper limit of normal in at least 2 subjects;
- 3. Two-fold increase in creatinine in at least 2 subjects;
- 4. Gastrointestinal (GI) bleed in at least 1 subject;

- 5. New onset atrial fibrillation in at least 1 subject in which case the Safety Review Committee will determine if dose escalation can be undertaken with additional monitoring (such as telemetry)
- 6. Clinically significant decrease in hemoglobin in at least 2 subjects;
- 7. Platelet count drop to less than 60,000 in at least 2 subjects;
- 8. Fifty percent drop in total white blood cell (WBC) count in at least 2 subjects; or
- 9. Two-fold increase in International Normalized Ratio (INR) in at least 2 subjects.

### **3.6** Stopping Rules for Study Discontinuation

The study will be discontinued if a serious adverse event (SAE) occurs that is deemed directly related to study drug by the Safety Review Committee. In the event of an SAE the safety committee will meet to determine if a stopping rule for study termination has been met and if so will stop the study before any other subjects are dosed.

Serious adverse events include: death, respiratory distress requiring hospitalization (acute respiratory distress syndrome [ARDS], pulmonary edema, pulmonary embolus, hemoptysis), GI bleed requiring blood transfusion, intracranial hemorrhage or stroke, renal failure requiring dialysis, MI, heart failure, ventricular tachycardia (torsades), heart block requiring temporary or permanent pacemaker, anaphylaxis, exfoliative dermatitis.

### 4 SUBJECT SELECTION

### 4.1 Inclusion Criteria

All volunteers must satisfy the following criteria to be considered for study participation.

- 1. Male or female.
  - a) Female subjects must not be of childbearing potential. Women are not considered of childbearing potential if one of the following is reported and documented on the medical history:
    - Postmenopausal with spontaneous amenorrhea for at least 1 year, or spontaneous amenorrhea for less than 1 year with serum follicle-stimulating hormone (FSH) levels >40mIU/ml; or
    - Surgically sterile (bilateral tubal ligation, hysterectomy, bilateral oophorectomy) at least 6 months prior to Screening.
  - b) Male subjects must have a history of vasectomy greater than 6 months, or use a double-barrier local contraception (i.e., spermicidal gel plus condom) when

Gossamer Bio, Inc.

engaging in sexual activity with women of childbearing potential while on study medication and for 28 days after the last dose of study medication.

- 2. Subject must be between 18 and 55 years of age (inclusive).
- 3. Subject's body mass index (BMI) must be between 18 and 32 kg/m^2 (inclusive), and subject must weigh a minimum of 50 kg (110 lbs).
- 4. Subject must voluntarily consent to participate in this study and provide their written informed consent prior to start of any study-specific procedures.
- 5. Subject is willing and able to remain in the study unit for the entire duration of the confinement period (or periods) and return for outpatient visits.
- 6. Subject must be a non-smoker.
- 7. Subject must demonstrate ability to use a dry powder inhaler effectively.

### 4.2 Exclusion Criteria

Subjects will be excluded for any of the following.

- 1. Hospitalization within the 6 months prior to the first dose of study treatment.
- 2. History or presence of clinically significant cardiovascular, pulmonary, hepatic, renal, hematologic, GI, endocrine, immunologic, dermatologic, neurologic, oncologic, or psychiatric disease or any other condition that, in the opinion of the Investigator, would jeopardize the safety of the subject or the validity of the study results.
- 3. History or presence of active lung disease (i.e., asthma, chronic obstructive pulmonary disease [COPD], pulmonary fibrosis, hemoptysis, bronchiectasis) or prior intubation.
- 4. Currently uses an inhaler.
- 5. History or presence of heart disease (i.e., prior myocardial infarction [MI], coronary artery disease, heart failure, hypertension, pulmonary hypertension, valve disease, atrial fibrillation, other arrhythmia, or prolonged QT syndrome).
- 6. History or presence of cancer (with the exception of basal cell skin cancer that has been effectively treated).
- 7. History of diabetes mellitus.
- 8. History of thyroid disease other than hypothyroidism control with levothyroxine and documented normal thyroid-stimulating hormone (TSH).
- 9. History of tuberculosis, Lyme disease, or other chronic or opportunistic infection.

- 10. History of positive purified protein derivative (PPD) skin test, or positive PPD test at screening.
- 11. Has a positive test for hepatitis B surface antigen, hepatitis C antibody, or human immunodeficiency virus (HIV) at screening or has been previously treated for hepatitis B, hepatitis C, or HIV infection.
- 12. History of smoking within the past 15 years.
- 13. Is a female with a positive pregnancy test result, or who has the ability to become pregnant, or who is lactating.
- 14. Has forced expiratory volume in 1 second (FEV1) less than 80% predicted, forced vital capacity (FVC) <80% predicted, or resting oxygen saturation less than 97% on room air at screening or baseline.
- 15. Upper respiratory infection within the 3 months prior to the first dose of medication.
- 16. History of major bleeding or major surgical procedure of any type within 6 months prior to the first dose of medication.
- 17. History of minor bleeding disorders such as epistaxis, rectal bleeding (spots of blood on toilet paper), and gingival bleeding within 3 months before the study treatment.
- 18. History of bleeding disorder or coagulopathy.
- 19. Females with history of dysfunctional uterine bleeding, including history of menorrhagia or metrorrhagia, unless subject has had a hysterectomy.
- 20. History of GI bleed.
- 21. Has used any over-the-counter (OTC) medication, nutritional or dietary supplements, herbal preparations, or vitamins within 7 days prior to the first dose of medication.
- 22. Has used any antiplatelet agents such as acetylsalicylic acid (ASA), nonsteroidal anti-inflammatory drugs (NSAIDs), clopidogrel (or similar agent) or anti-coagulants within 7 days prior to the first dose of medication.
- 23. Has used any prescription medication, except female hormonal replacement therapy, within 14 days prior to the first dose of study medication.
- 24. Has been treated with any known drugs that are moderate or strong inhibitors/inducers of CYP enzymes such as barbiturates, phenothiazines, cimetidine, carbamazepine, etc., within 30 days prior to the first dose of study

Gossamer Bio, Inc.

medication and that in the Investigator's judgment may impact subject safety or the validity of the study results.

- 25. History of peripheral vascular disease.
- 26. History of autoimmune or collagen vascular disease.
- 27. History of sleep apnea.
- 28. History of clinically significant allergy to medications.
- 29. History of anaphylaxis.
- 30. History of liver disease
- 31. History of alcohol or drug abuse.
- 32. Prolonged QTc on 12-lead ECG (i.e., QTc corrected using Fridericia's formula [QTcF] >450 msec), PR >210 msec, or QRS >110 msec at screening.
- 33. Evidence of prior MI on ECG; presence of atrial fibrillation on ECG; presence of pre-excitation, 2nd or 3rd degree heart block, or abnormal waveform morphology that would preclude accurate measurement of the QT interval duration or other clinically significant abnormalities.
- 34. Chest x-ray reveals presence of infiltrate or other abnormality (mass, granuloma, fibrosis, pulmonary thickening, pleural effusion, pulmonary edema, wide mediastinum, cardiomegaly, or clinically significant increased interstitial markings).
- 35. History of neurologic disorder (i.e., multiple sclerosis, amyotrophic lateral sclerosis [ALS], cerebrovascular accident [CVA], transient ischemic attach [TIA])
- 36. History of deep vein thrombosis or pulmonary embolus.
- 37. History of clotting disorder.
- 38. History of mental illness requiring drug treatment or hospitalization.
- 39. History of renal failure or proteinuria (defined as 2+ proteinuria: ≥100 mg/dL on isolated urinalysis).
- 40. Test results greater than the upper limit of normal (ULN) for AST, ALT, or total bilirubin
- 41. Test results greater than the upper limit of normal on the following coagulation tests: INR, prothrombin time (PT), or partial thromboplastin time (PTT).
- 42. Total cholesterol >250 mg/dL or triglycerides >300 mg/dL at screening (based on fasting lipid profile).

Gossamer Bio, Inc.

- 43. Estimated creatinine clearance less than 60 mL/min at the screening visit using the Modification of Diet in Renal Disease (MDRD) equation.
- 44. Hemoglobin at screening of <11.5 g/dl (if female subject) or <12.5 g/dl (if male subject).
- 45. Has a clinically significant abnormal finding on the physical exam, medical history, electrocardiogram (ECG), or clinical laboratory results at screening. Note: Subjects with abnormal laboratory results not specifically excluded by this protocol may be enrolled if the Investigator deems the out-of-range values as not clinically significant.
- 46. History of treatment with a kinase inhibitor.
- 47. Has been on a significantly abnormal diet during the 4 weeks preceding the first dose of study medication.
- 48. Has donated blood or plasma within 30 days prior to the first dose of study medication.
- 49. Has participated in another clinical trial (randomized subjects only) within 30 days prior to the first dose of study medication.
- 50. Has a positive urine screen for drugs of abuse (amphetamines, barbiturates, benzodiazepines, cocaine, cannabinoids, opiates) or cotinine.
- 51. Vital signs (measured sitting after 3 minutes rest) at screening that are not within the following ranges (inclusive): heart rate: 40–100 beats per minute [bpm]; systolic blood pressure (BP): 90–145 mmHg; diastolic BP: 50–95 mmHg. Out-of-range vital signs may be repeated once. Blood pressure will be measured in both arms at screening, with a 3-minute rest between each measurement. Predose vital signs will be assessed by the Principal Investigator or designee (e.g., a medically qualified sub-investigator) prior to study drug administration. The Principal Investigator or designee will verify the eligibility of each subject with out-of-range vital signs and document approval prior to dosing.
- 52. Significant difference (i.e., greater than 15 mmHg) between the systolic blood pressure in each arm at screening.
- 53. History of lactose intolerance.

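### Exclusion 49 tests whether a recent trial participant was randomized, not whether they were dosed, so read literally it misses volunteers given an investigational product in a non-randomized trial

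*Protocol*

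**What the plan says.** Protocol Section 4.2, item 49, excludes a volunteer who "Has participated in another clinical trial (randomized subjects only) within 30 days prior to the first dose of study medication". It is the only criterion in the protocol that addresses participation in another trial.

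The neighbouring criteria on prior drug use are written by product type. Item 23, for example, reads "Has used any prescription medication, except female hormonal replacement therapy, within 14 days prior to the first dose of study medication".

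Section 1.1 states that "PK10571 has not been previously studied in humans". Under Section 3, each cohort has 6 active and 2 placebo subjects. It starts with a sentinel pair (one active, one placebo), whose tolerance is evaluated before the other six are dosed.

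The SAP has no rule on prior investigational exposure. Its Section 6.9 only lists prior and concomitant medications.

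**The concern.** A washout for earlier trial participation guards against carry-over from another investigational drug, so the natural test is whether a product was received. Item 49 tests randomization instead. Someone dosed in a single-arm, open-label or fixed-sequence trial was never randomized and falls outside the rule, however recent the dose.

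Safety and tolerability lead the study's objectives, and the cohorts are small. A residual effect of another investigational product could appear in the adverse event, laboratory or ECG data, or could alter PK10571 exposure, with little to show where it came from. The assessors are blinded, and Section 6.3 leans heavily on temporal sequence when judging relatedness. The volunteer would also be exposed to two investigational products within a short time.

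**Working it through.** The point turns on wording, so the check is to read item 49 literally and then look for another rule that would catch the same person. The test case is a volunteer given an unapproved drug, not a kinase inhibitor, in a non-randomized trial within the 30 days before first dose.

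| Section 4.2 item | Wording or content | Window | Catches the test case? |
|---|---|---|---|
| 49 | "Has participated in another clinical trial (randomized subjects only) within 30 days prior to the first dose of study medication" | 30 days | No: not randomized |
| 21 | "Has used any over-the-counter (OTC) medication, nutritional or dietary supplements, herbal preparations, or vitamins within 7 days prior to the first dose of medication" | 7 days | No, unless the product is an OTC or supplement type |
| 22 | Antiplatelets, NSAIDs, anticoagulants | 7 days | Only if in these classes |
| 23 | "Has used any prescription medication, except female hormonal replacement therapy, within 14 days prior to the first dose of study medication" | 14 days | Only marketed prescription drugs, on its plain meaning |
| 24 | "Has been treated with any known drugs that are moderate or strong inhibitors/inducers of CYP enzymes" | 30 days | Only if that property is known and the Investigator judges that it matters |
| 46 | "History of treatment with a kinase inhibitor" | Any time | No: other drug class |
| 2 | "any other condition that, in the opinion of the Investigator, would jeopardize the safety of the subject or the validity of the study results" | None | Only by Investigator judgement |
| 45 | Clinically significant abnormal screening findings | Screening | Only if a finding is present and judged significant |

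The remaining exclusions do not bear on prior investigational drugs. Outside Section 4.2:

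- Section 4.3 (restrictions) does not mention investigational products.
- Section 4.4 takes a medication history, so the exposure could come to light, but it attaches no rule to that finding.
- Section 5.3 asks subjects at check-in to affirm that the exclusions and restrictions have not been violated. It therefore inherits the gap.

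No categorical rule covers the test case.

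**Weight of one subject**, from the allocation in Protocol Section 3:

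- Active arm of a cohort: 1/6 = 16.7%.
- Active sentinel: 1 of 1.
- Placebo: SAP Section 6.3 groups placebos in the summary tables. With 2 per cohort, Part A has 4 × 2 = 8 to 5 × 2 = 10 placebo subjects, and a full Part B has 3 × 2 = 6. One subject is then 1/8 = 12.5% to 1/10 = 10% in Part A, and 1/6 = 16.7% in Part B.

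These shares would apply to any unsuitable subject. They show how sensitive a small cohort is, not how likely this problem is.

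**Link to escalation.** Two Section 3.5 criteria are framed for a single subject: item 4 ("Gastrointestinal (GI) bleed in at least 1 subject") and item 5 (new atrial fibrillation). The lead sentence of Section 3.5 makes every criterion conditional on the Safety Review Committee judging the event related to study drug. Item 5 also leaves the Committee to decide whether escalation can go on with added monitoring. One confounded event can therefore enter the deliberation without settling it.

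**The case against.** The strongest case against the point is that item 49 is loosely drafted and little harm follows. A site may well read randomized as enrolled and not merely screened. The Investigator can refuse a recently dosed volunteer under item 2, and the medication history gives an opportunity to learn of the dose. Items 22, 23, 24 and 46 would remove many such volunteers, including some from fixed-sequence interaction studies that use marketed drugs or known CYP inhibitors or inducers. Nothing in the documents shows that such a person was, or was meant to be, admitted.

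Most of this stands, and it limits the point. It does not remove it: a rule that works only if the site reads it differently, or if discretion repairs it, does not do its job as written.

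Four stronger readings are tempting, and the documents do not support them:

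- *Such a volunteer is simply eligible.* They are not excluded by any categorical criterion, but item 2 still allows refusal.
- *One such volunteer could alone meet a stopping criterion.* The relatedness judgement in Section 3.5 rules this out.
- *One such volunteer is half of the placebo comparison.* That is true of allocation within a cohort, but not of the summaries, where placebos are grouped.
- *Carry-over would be attributed to PK10571 or placebo.* It could be. However, Protocol Section 6.3 allows other factors to be weighed. SAP Sections 6.12.2, 6.12.3 and 6.12.5 also report change from a predose baseline (SAP Section 6.2.3), which would absorb a stable residual effect, though not a fading or delayed one.

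**Conclusion.** The point holds as a gap in wording. Item 49 does not do what a prior-trial washout is for, and no other criterion categorically covers an unapproved, non-kinase drug given in a non-randomized trial.

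The consequence is possible confounding in a first-in-human study where one subject is 17% of a cohort's active arm and may be the only active sentinel. It could influence an escalation decision but not force one.

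This rests on two assumptions: that item 49 is applied as written, and that prescription medication in item 23 does not include unapproved products. The documents do not say how often such volunteers present, so no expected number of affected subjects can be given. This is a cheap improvement, not a flaw that undermines the design.

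**What to change.** In Section 4.2, item 49, replace the parenthesis with wording that covers anyone who was randomized or received any investigational product in the other trial. Keep the protocol's own 30-day window. People who only failed screening elsewhere stay eligible, which is presumably what the parenthesis was for.

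The cost is one phrase in the next amendment and a slightly smaller volunteer pool. The benefit reaches only subjects not yet enrolled: SAP Section 6.2.10 describes some Part A samples as already collected before an amendment, so part of the study had run under the existing wording.
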